1 STUDY SYNOPSIS

Study Title	EXercise TheRApy in Mesothelioma – A feasibility study (EXTRA-Meso feasibility study)
Study Sponsor	NHS Greater Glasgow and Clyde
Study Design	Randomised feasibility trial
Number of Patients	40
Patient Population	Patients with a diagnosis of mesothelioma
Primary Objective	To determine the feasibility of recruiting patients with mesothelioma to a randomised trial of exercise therapy, in order to inform design of a future phase 3 trial
Secondary Objectives	
 1. To determine barriers to study recruitment 2. To determine barriers to study retention 3. To determine safety and tolerability of the exercise programme intervention and study assessments
Primary Outcome Measure	Number of patients recruited
Secondary Outcome Measures	
 1. Proportion of screened patients who are ineligible 2. Reasons for study ineligibility 3. Study drop-out rate 4. Reasons for study drop-out 5. Intervention adherence rate 6. Adverse events 7. Health-related Quality of Life (HRQoL) questionnaire completion rate 8. Framework analysis from qualitative interviews
Eligibility Criteria	
Inclusion Criteria:
 
 1. Diagnosis of mesothelioma, ratified by a mesothelioma MDT 2. Performance status 0 -2 3. Clinical frailty score ≤ 5 4. Informed written consent 
Exclusion Criteria:
 
 1. Performance status ≥ 3 2. Clinical frailty score ≥ 6

	3. Unlikely to be able to participate in an exercise programme (clinician/physiotherapist judgement)
Screening and Consent	Patients with mesothelioma will be identified at mesothelioma MDTs, routine respiratory/oncology outpatient appointments, and during inpatient reviews. Those meeting all eligibility criteria will be provided with a Patient Information Sheet (PIS) and given sufficient time to consider participation.
Randomisation and Allocation	Following consent and baseline assessments, patients will be randomised using an online system (sealedenvelope.com) and allocated 1:1 using random permuted blocks to one of two groups: 
 A. Exercise Therapy B. Standard Care
End of Study	Trial participation will end when the last patient has completed their 26 week visit
Study duration	18 months

2 ABBREVIATIONS

MPM	Malignant Pleural Mesothelioma
WoS	West of Scotland
HRQoL	Health-related Quality of Life
SD	Standard deviation
PS	Performance Status
CFS	Clinical Frailty Score
PIS	Patient Information Sheet
MDT	Multi-disciplinary team
FBC	Full blood count
CRP	C-reactive protein
6MWD	6 minute walk distance
STS	Sit to stand
BMI	Body mass index
MUST	Malnutrition universal screening tool
(S)WEMWBS	Short Warwick Edinburgh Mental Wellbeing Scale
HADS	Hospital anxiety and depression scale
SF-36	36-item short form survey
EQ-5D-5L	EuroQol group 5 item survey
EORTC-QLQ-C30	European organisation for research and treatment of cancer survey
SACT	Systemic anti-cancer therapy
CNS	Clinical Nurse Specialist
PROMs	Patient related outcome measures

3 STUDY FLOWCHART

4 SUMMARY OF STUDY

4.1 Plain English Summary

Malignant pleural mesothelioma (MPM) is an aggressive, strongly associated with asbestos exposure. It most frequently affects the lining of the lung (pleura), but can also affect the other parts of the body, including the lining of the heart and abdomen. The incidence of MPM has been increasing over the last decade, despite legislative control of industrial asbestos use, due to a long latency period between initial exposure and development of the disease, and is predicted to continue to increase over the next 5 – 10 years.

Patients with MPM often experience troublesome symptoms including breathlessness, pain and fatigue. They can also experience anxiety and depression and feel like their quality of life is worse than before they were diagnosed. Sarcopaenia is a complex condition, where there is an interplay between inflammation and cancer, which ultimately results in low skeletal muscle mass.

Malnutrition and sarcopaenia is common in individuals with MPM, and is associated with worse outcomes, including in those who get chemotherapy.

Unfortunately, the average life expectancy following a diagnosis of mesothelioma is approximately 12 months. Currently, treatment in patients who are fit enough is aimed at prolonging this life expectancy, and involves drug treatment in the form of either chemotherapy or more recently immunotherapy. Whether a person with mesothelioma receive this treatment can depend on their physical fitness.

Exercise Therapy

Improving health-related quality of life (HRQoL) and physical fitness is a key goal for all patients with MPM, and maximising treatment opportunity has never been more important, following the recent approval of immunotherapy for the treatment of MPM across the UK. Exercise therapy is a rational approach to improving HRQoL and could also improve and/or maintain physical fitness to allow more patients to ultimately receive treatment. There is a growing body of evidence that exercise therapy in other cancers, such as lung cancer, can improve cardio-respiratory fitness, muscle mass, muscle strength, anxiety levels and HRQoL. Exercise may also have a role in breaking the vicious cycle of cancer, inflammation and sarcopaenia. The Prehab4Cancer programme is a successful initiative launched in Greater Manchester for patients with lung cancer. Patients who take part in the programme have reported improvement in their functional fitness and quality of life. We also know that home-based rehabilitation programmes are safe in patients with MPM. However, there is no evidence on the potential benefits of a tailored exercise and nutritional support intervention in mesothelioma. This is the focus of the current study and a planned future phase 3 trial.

EXTRA-Meso Feasibility Study

An exercise intervention study such as this one has never been done in mesothelioma. Before planning a larger phase 3 randomised controlled trial, we are conducting a smaller study to ensure that running an exercise trial in patients with mesothelioma is feasible. This study will determine this feasibility, the number of centres that will likely be needed to recruit to a larger study and define the optimum duration and format of the exercise intervention itself.

4.2 Scientific Summary

High symptom burden, anxiety and depression are common in Malignant Pleural Mesothelioma (MPM), even in those with good performance status (PS). (1,2) Patients with MPM often report poor health-related quality of life (HRQOL), which is itself, associated with poorer survival. (3,4) The treatment of MPM typically involves systemic anti-cancer therapy (SACT), receipt of which may be associated with better maintenance of HRQOL compared with those who decline, as previously reported in the SWAMP trial. (5) However, chemotherapy uptake in MPM is low, often due to reduced physical fitness in patients who are frequently in their 7th or 8th decade of life.

Maximising HRQOL is a key goal for all MPM patients and maximising treatment opportunity has never been more important, following the recent approval of combination immunotherapy, regardless of histology, across the UK. Combination nivolumab and ipilimumab significantly improves overall survival in unresectable MPM compared to standard chemotherapy in the first-line setting. (6) This survival benefit appears amplified in patients with non-epithelioid histology, with maintenance or improvement in HRQOL in responding patients. (7) This is particularly important in this sub-group, in whom standard chemotherapy is rarely effective and symptom burden is frequently high with poor HRQOL. (5)

Exercise therapy is a rational approach to improving HRQOL and could also maximise treatment opportunities in MPM. This reflects a growing body of evidence for exercise interventions in other cancers and particular features of deconditioning associated with MPM recently identified by our group. In non-small cell lung cancer (NSCLC), pre-operative exercise therapy in patients undergoing resection is associated with improved cardio-respiratory fitness, reduced post-operative complications and improved HRQOL. (8) Olivier et al also reported that a home pulmonary rehabilitation programme was safe and feasible in patients with lung cancer and a small number of patients with MPM (n=17). (9) Our group has recently reported that low skeletal muscle mass (sarcopaenia), a feature of the cancer cachexia syndrome is independently associated with adverse survival. This effect was more marked on in thoracic musculature ipsilateral to the tumour (10) and was observed if sarcopaenia was present prior to starting chemotherapy and if patients lost skeletal muscle mass during treatment. (11) These features suggesting a dynamic deconditioning effect, driven directly by MPM, which could be predicted and modified to improve outcomes. In these studies, the presence of sarcopaenia was also notably associated with systemic inflammation. (11)

A recent systematic review and meta-analysis has confirmed poorer progression-free survival and overall survival in patients with sarcopaenia pre-immunotherapy in solid tumours including lung cancer and melanoma. (12) In MPM, malnutrition and 'pre-sarcopaenia' has previously been reported in 38% and 54% respectively, with lower activity levels in pre-sarcopenic patients. (13) Exercise intervention in patients with sarcopaenia may improve muscle mass, muscle strength and physical performance. (14) There is also evidence that exercise may have a role in breaking the vicious cycle of cancer, inflammation and cachexia (15). Furthermore, there is evidence that exercise improves quality of life and reduces anxiety in patients with other cancers. (16,17) The 'Prehab 4 Cancer' programme, which this study will be utilising, reported improvements in functional fitness and quality of life in patients with NSCLC. (18) However, there is no evidence regarding the potential

benefits of a tailored exercise and nutritional support intervention in mesothelioma. This is the focus of the current study and the planned future phase 3 trial.

5 STUDY OBJECTIVES

5.1 Primary Objective

- To determine the feasibility of recruiting patients with mesothelioma to an exercise therapy study

5.2 Secondary Objectives

- To determine barriers to study recruitment
- To determine barriers to study retention
- To determine safety and tolerability of the exercise intervention and study assessments

6 STUDY DESIGN

This study is a prospective randomised feasibility study, randomising patients 1:1 to exercise therapy intervention versus standard care.

6.1 Study Setting

Patients will be recruited from two mesothelioma centres, the NHS Greater Glasgow and Clyde Glasgow Pleural Disease Unit and Wythenshawe Hospital, Manchester NHS Foundation Trust. These two centres have high rates of mesothelioma. The West of Scotland (WoS) has had between 65 – 75 new diagnoses of mesothelioma per year over the last 3 years (data from the Scottish National Mesothelioma MDT). Similarly, Greater Manchester have seen approximately 50 cases of mesothelioma per year between 2016 – 2018 (data from the National Mesothelioma Audit). The Glasgow Pleural Disease Unit hosts the Scottish National Mesothelioma MDT, where cases across Scotland are discussed. Wythenshawe Hospital hosts the Greater Manchester regional mesothelioma MDT. This set up at both recruiting centres ensures that all patients diagnosed within the West of Scotland or Greater Manchester can be considered for this trial. Both centres have successfully collaborated on numerous research studies, have a proven track record in recruiting patients to mesothelioma trials and have appropriate research infrastructure in place to deliver this study.

6.2 Study Population

6.2.1 Inclusion Criteria

1. Diagnosis of mesothelioma ratified by Mesothelioma MDT
2. ECOG performance status (PS) 0 – 2
3. Clinical Frailty Score (CFS) ≤5
4. Informed consent

6.2.2 Exclusion Criteria

1. ECOG Performance Status >2

2. Clinical Frailty Score ≥ 6
3. Unlikely to be able to participate in an exercise programme (clinician/physiotherapist judgement)

6.2.3 Identification of participants and consent

Patients will be screened at the respective mesothelioma MDTs and/or identified at respiratory and/or oncology outpatient clinics and/or at inpatient review. Potential participants who meet the eligibility criteria will be approached by a member of the study team. If interested, the patient will be provided with the study Patient Information Sheet (PIS) and given sufficient time to read it, discuss with their family, if they wish, and ask questions before being invited to provide informed written consent to enrol in the study. If a patient has a virtual (telephone or video) appointment, remote “witnessed verbal consent” can be taken. For witnessed verbal consent to be valid, the participant must be witnessed by two members of the research team to agree to each point of the consent form. Both research team members must then sign the consent form and indicate on the form that the consent was taken remotely. All consent documentation will be scanned into the patient’s clinical notes. Detailed screening logs will be kept to record reasons for non-enrolment. Should the patient read the patient information sheet but decline to take part, they may be asked to consent to a semi-structured interview with a member of the study team, to explore their reasons for declining to participate, in order to inform future study design. Potential participants who decline to participate will be signposted to locally available community activities and services that are available to promote long-term health improvement if they wish. There is no time limit on time of diagnosis to study enrolment.

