6.3 Sample size calculation

The current feasibility study will aim to recruit 40 patients. No formal sample size is feasible or appropriate, but this number is sufficient to allow identification of barriers to recruitment and retention (the latter informing the likely drop-out rate for the future phase 3 trial) and the duration and design of the exercise therapy intervention.

The primary objective of the future phase 3 trial will be to determine whether exercise therapy results in a clinically meaningful improvement in HRQOL at 16 weeks post-randomisation. Assuming a mean population score of 60 (SD 20) based on QoL scores previously reported in other mesothelioma studies, we currently estimate that a sample size of 84 patients in each arm is required to detect a 10-point improvement in EORTC QLQ C30 quality of life scores, with 90% power at 5% two-sided significance level. With a currently assumed 25% drop-out rate, based on the ‘Prehab4Cancer’ dropout rate in patients with NSCLC, we estimate that we would require a total sample size of 224 patients. Data from the current feasibility study will (a) provide a more robust estimate of baseline mean HRQOL score (based on the population score recorded from all patients at baseline assessment), (b) allow a more precise estimate of drop-out rate based on an optimised exercise intervention and (c) allow us to calculate the number of centres needed based on the recruitment rate achieved.

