7 BASELINE ASSESSMENT

Having provided written or witnessed verbal informed consent to participate in the study, participants will all undergo the same baseline assessment. This will include recording of:

- Patient demographics, disease characteristics, including subtype and stage, co-morbidities and medication history (including current or prior systemic anti-cancer therapy).
- Routine blood results, including full blood count (FBC), C-reactive protein (CRP) and albumin
- Body Mass Index (BMI) and malnutrition universal screening tool (MUST) score
- Functional fitness measurements in the form of:
 - Hand grip strength
 - 6 minute walk distance (6MWD)
 - 30 second sit-to-stand (STS) test
- Patient related outcome measures (PROMs) via completion of the following questionnaires related to HRQoL, wellbeing and symptoms:
 - Euroquol quality of life survey (EQ-5D-5L)
 - 36-item short form survey (SF-36)
 - European organisation for research and treatment of cancer (EORTC) QLQ-C30
 - Hospital Anxiety and Depression Scale (HADS)
 - Short Warwick Edinburgh Mental Wellbeing Scale ((S)WEMWBS)
- Presence/absence of features of sarcopenia utilising:
 - Strength, assistance with walking, rising from a chair, climbing stairs, and falls (SARC-F) screening questionnaire

- Skeletal muscle area and visceral fat index measurements on routinely-acquired clinical CT scan within the preceding 3 months

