10 STATISTICAL ANALYSIS PLAN

We will use descriptive statistics to describe the demographics and clinical characteristics of the study population. Means (with standard deviations) or medians (with inter-quartile ranges) will be used to summarise continuous variables, depending on their distribution and proportions to summarise categorical variables.

Total recruitment, recruitment rate, study drop-out rate and intervention adherence rate will be reported by simple descriptive statistics, or proportions where appropriate.

Semi-structured interviews will be analysed using Framework Analysis¹⁹, which will involve a five-step process:

1. Familiarisation with the data
2. Identifying a thematic framework
3. Indexing
4. Charting
5. Mapping and interpretation

The analysis will be predominantly deductive, as it will specifically focus on facilitators and barriers to study retention, and to the uptake and experience of the exercise intervention.

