11 END OF TRIAL

Trial recruitment will terminate either 12 months after opening or after 40 patients have been recruited, whichever is soonest. Trial participation will cease once the final patient has completed their 26-week follow-up.

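### With no limit on time since diagnosis, a single pooled recruitment rate may include a one-off pool of existing patients and may understate the number of phase 3 centres.

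*Combined protocol and SAP*

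**What the plan says.** On eligibility, Section 6.2.3 states: "There is no time limit on time of diagnosis to study enrolment". Besides MDT screening, patients may be "identified at respiratory and/or oncology outpatient clinics and/or at inpatient review". The Section 7 baseline record covers medication history, "including current or prior systemic anti-cancer therapy", so patients already under treatment are expected to enter. Section 7 asks for disease characteristics such as subtype and stage but does not name date of diagnosis.

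On the recruitment window, Section 11 states: "Trial recruitment will terminate either 12 months after opening or after 40 patients have been recruited, whichever is soonest".

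On use of the rate, Section 6.3(c) says the study's data will "allow us to calculate the number of centres needed based on the recruitment rate achieved". Section 4.1 also lists the number of centres among the things the study will determine.

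On analysis, Section 10 states: "Total recruitment, recruitment rate, study drop-out rate and intervention adherence rate will be reported by simple descriptive statistics", or by proportions where appropriate. No section plans to report recruitment by calendar month or by time since diagnosis. The documents give no phase 3 recruitment period, no phase 3 rule on time since diagnosis, and no statement on whether these two centres would take part again.

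**The concern.** When a site opens, it can approach eligible patients who were diagnosed earlier and are still alive, as well as new cases. The existing patients are a stock that each site can draw on once, while new cases are a flow that continues. The feasibility window covers only the opening period, when the stock is available. A pooled rate over that window can therefore exceed the rate a site would sustain later.

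The centre number is one of three inputs to phase 3 that Section 6.3 says the study will supply. If the pooled rate is carried forward over a longer period, phase 3 could open with too few centres. If diagnosis dates have not been collected, including for eligible patients who declined, the two components may be hard to separate afterwards.

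**Working it through.** **The plan's own figure.** Section 6.3 uses SD 20, a 10-point difference, 90% power and 5% two-sided significance. Per arm, n = 2 × [20 × (1.960 + 1.282) / 10]² = 84.06, against 84 stated; power at 84 per arm is 0.900. Allowing for 25% drop-out, 168 / 0.75 = 224, as stated. The documents give no centre number, so 224 is the only fixed input to one.

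**Possible size of the pool.** Section 6.1 gives 65 to 75 new cases a year in the West of Scotland and about 50 in Greater Manchester, together 115 to 125. Section 4.1 says "the average life expectancy following a diagnosis of mesothelioma is approximately 12 months". Assume steady state and exponential survival. Living diagnosed patients at opening then equal incidence × mean survival. Mean survival (m) is 1.0 year if 12 months is a mean, and 1/ln 2 = 1.44 years if it is a median. That gives 115 to 125 patients, or 166 to 180, before the performance status, frailty and exercise-ability criteria are applied.

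**Effect on the rate.** Let f be the recruitability of existing patients relative to new cases; the documents give no value. If the pool is used up in year 1, the year-1 rate divided by the later rate is 1 + f × m. Assume the target of 40 is met in 12 months at two centres, which is 20 per centre.

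**Centres for 224 patients over two years (period assumed).** The pooled rate gives 224 / (20 × 2) = 5.6, so 6 centres. If each new centre has its own pool once, the yield per centre is 20 + 20 / (1 + f × m). Ranges run from m = 1.0 to m = 1.44.

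| f | Year-1 / later rate | Later rate per centre-year | Two-year yield per centre | 224 / yield | Centres |
|---|---|---|---|---|---|
| 10% | 1.10–1.14 | 18.2–17.5 | 38.2–37.5 | 5.87–5.98 | 6 |
| 25% | 1.25–1.36 | 16.0–14.7 | 36.0–34.7 | 6.22–6.46 | 7 |
| 50% | 1.50–1.72 | 13.3–11.6 | 33.3–31.6 | 6.72–7.08 | 7–8 |
| 100% | 2.00–2.44 | 10.0–8.2 | 30.0–28.2 | 7.47–7.95 | 8 |

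**Other phase 3 designs.**
- Fresh centres, same eligibility, 12 months: 224 / 20 = 11.2, so 12 centres whether or not the pool is separated. There is no bias.
- No pool available (time since diagnosis restricted, or these sites reused after depletion), two years: centres = 224 / [20 × (1 − b) × 2], where b is the pool's share of year-1 recruits. For b = 10%, 25%, 40% and 60% this gives 7, 8, 10 and 14.
- Early stop at 40: if 40 are reached in 8 months and the rate uses elapsed time, it is 30 per centre-year. Then 224 / 60 = 3.7, so 4 centres over two years, from a shorter window in which any pool could weigh more.

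**Which split to use.** Suppose there is no pool effect and every patient enrols exactly 3 months after diagnosis. Recruitment is flat from the first day, yet 3/12 of the year's recruits were diagnosed before opening. Labelling them as backlog projects 0.75 × 2 + 0.25 = 1.75 years' yield over two years instead of 2.0, which is 12.5% too low. A split at site opening would therefore overstate the centres needed.

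**The case against.** A reader might infer that the pooled rate will necessarily give too few centres. The documents do not support that. It requires a longer phase 3 recruitment period, a limit on time since diagnosis, or reuse of these sites, and none of these is stated. Slow site start-up would push the rate the other way.

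A reader might also infer that the plan commits to one unadjusted overall rate. Sections 6.3 and 10 do not rule out monthly reporting or adjustment at the phase 3 planning stage. Section 6.2.3 requires detailed screening logs, and MDT ratification is an entry criterion, so diagnosis dates may be recoverable. This softens the point, but neither the split nor the date field is planned.

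The size is also uncertain. Recruitability of 25% or more has no basis in the documents. With survival of about a year, many existing patients may no longer meet the fitness criteria, and at 10% the two-year answer does not move. The pool need not be exhausted if recruitment stops early at 40. A shift of one or two centres lies within sampling error: the exact Poisson 95% interval for 40 recruits is 28.6 to 54.5, which gives 8 down to 5 centres over two years. That limits the practical weight of the bias, but it does not remove it.

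Finally, no analysis of this trial becomes wrong. The progression criteria in Section 13 use total recruitment and adherence, not a centre number. That stands.

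**Conclusion.** The point holds in conditional form. Open eligibility and a short opening window mean the observed rate may contain a one-off pool, and the plan has no step to separate it before the rate is used for the centre number. Whether the centre number is too low depends on phase 3 features that the documents leave open.

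Under the illustration's assumptions the two-year shift is from none to two centres on a base of 6. It is larger if no pool is available in phase 3, and absent for fresh centres recruiting for about 12 months under unchanged eligibility. Survival shape, relative recruitability, year-1 yield and phase 3 duration are all assumptions, so these counts are not an expected effect. This is a weakness in what can be inferred for phase 3, not an arithmetic error, and it is cheap enough to correct that it should be.

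**What to change.** - **Data (Sections 6.2.3 and 7):** record date of diagnosis on the CRF, and on the screening log for every eligible patient approached, including those who decline.
- **Section 10:** report recruitment per centre by calendar month and by time since diagnosis at enrolment, with the number randomised out of eligible patients approached in each group. Do not split simply by diagnosis before or after site opening, because the normal lag to enrolment would then be counted as backlog.
- **Section 6.3(c):** base the centre number on the sustained rate that matches the phase 3 eligibility window and recruitment period, and add any opening pool once per new centre.

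The cost is one date field, one table and a sentence in Section 6.3. Eligibility and sample size do not change. The downside is precision: monthly and subgroup rates will rest on few patients, so they should be given with intervals and the centre number shown as a range.
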